3.4. Primary Study Endpoint

The primary endpoint is the correlation of the change of C5b-9 and change of platelet count from baseline (T0) to after 15 minutes of administration of protamine (T2).

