1. INTRODUCTION

1.1. Background

Patients undergoing coronary artery bypass graft surgery (CABG) frequently exhibit postoperative bleeding complications which are still a major cause for morbidity and mortality (1). One major contributing factor is the loss of platelets and impaired platelet function. During cardiopulmonary bypass (CPB) blood comes in close contact with foreign surfaces which induces a series of reactions; especially the complement system as part of the innate immunity is highly activated (2). Due to the strong crosslink between complement system, platelet function and the plasmatic coagulation it is likely that complement activation during CPB has an impact on the overall process of clot formation. (3). Besides the activation of the complement system there is growing evidence that the occurrence of mitochondrial DNA (mtDNA) during CPB might be related to further platelet activation (4). Activated platelets may enhance micro-thrombosis leading to organ failure and thereby contributing to postoperative morbidity.

Several studies investigated the effect of complement activation in cardiac surgery patients (2;5;6-7) however, it is still unclear whether the activation of the complement system further increases platelet loss.

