1.2. Need for the Study

One major complication during and after CABG surgery is bleeding requiring transfusion and even reoperation in about 2%- 8% of patients.

A recent study shows that impaired hemostasis was observed in 9,5 - 21,5% of these cases (1). As bleeding complications increase patient morbidity and mortality, this study is designed to investigate, the possible mechanisms of platelet loss during CABG.

We hypothesize that increased complement activation during CPB leads to platelet activation and loss of platelets. We further hypothesize that the degree of complement activation and levels of mtDNA correlate with postoperative bleeding, transfusion requirements and clinical outcome.

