3.2. Timetable

- T0 baseline: after insertion of arterial cannula beginning surgery
- T1 after re-opening aortic clamp on CPB
- T2 15 minutes after protamine infusion
- T3 end of surgery = admission lab at the postoperative intensive care unit
- T4 4 hours after surgery/admission
- T5 12 hours after surgery/admission
- T6 24 hours after surgery begin
- T7 48 hours after surgery begin
- T8 72 hours after surgery begin
- T9 30 days after surgery or hospital admission

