3.3.2. Collection of routinely measured laboratory parameters, and clinical data (T0-T9)

The following routine laboratory parameters will be collected if available:

activated clotting time (ACT), Rotem parameters, Multiplate test analysis, whole blood cell count, standard plasmatic coagulation tests, blood gas analysis, CRP, Procalcitonin (PCT), renal and liver function parameters, cardiac enzymes (CK, CK-MB, Myoglobin, Trop T, NTpro BNP)

Study related blood sampling will overlap with routine blood sampling.

Clinical Data

The following parameters will be collected at baseline(T0):

age, gender, body weight(kg) and size (cm), medical history (chronic renal impairment, Diabetes, Hypertension, previous myocardial infarction, previous stroke, previous percutaneous coronary intervention, previous CABG), pre-medication, Euroscore II.

During surgery following data will be collected if available:

Details on CPB, Cell Saver blood volume, blood pressure (BP), hear rate (HR), central venous pressure (CVP), mean pulmonary artery pressure (MPAP), cardiac index (C.I.), cardiac output (C.O.), Oxygen Saturation (SpO2), Horowitz, Fraction of inspired Oxygen (FiO2), Diuresis per hour, Concomitant Medication, transfusion and coagulation products, , need for extracorporeal membrane oxygenation (ECMO), need for inhalative NO

As appropriate, the above mentioned clinical data will be collected until POD3 (T1-T9).

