4. STUDY POPULATION

All adult patients undergoing elective coronary artery bypass graft surgery with written informed consent meeting the following criteria:

4.1. Inclusion criteria:

- I.1. Male and female subjects > 18 years and < 86 years
- I.2. elective coronary artery bypass graft surgery **with or without valve surgery (max. 2 valves)** and **elective valve surgery (max. 2 valves)** on cardiopulmonary bypass (CPB)
- I.3. ASA I - IV
- I.4. written informed consent

4.2. Exclusion criteria:

- E.1. emergency CABG **with or without cardiac valve surgery and emergency valve surgery and emergency aortic dissection**
- E.2. preexisting complement deficiency syndromes
- E.3. preexisting thrombocytopathy or thrombocytopenia (platelet count below 100 G/L)
- E.4. Known history of congenital coagulopathy
- E.5. Patients that are known to be pregnant
- E.6. Known participation in another interventional clinical trial

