7. STATISTICS

Primary analysis

The primary endpoint of this study is the correlation of the change in C5b-9 and the change in platelet count from baseline (T0) to 15 minutes after administration of protamine (T2). The analyzed study population will consist of all patients with available measurements necessary to assess the primary endpoint.

The two changes (C5b-9 and platelet count) are continuous variables and their correlation (Spearman's rank-order correlation denoted by ρ) will be assessed. Therefore, the hypotheses

$$H_0: \rho = 0 \quad \text{vs.} \quad H_1: \rho \neq 0$$

will be tested using the Spearman rank-order correlation test, i.e. the null hypothesis that the Spearman correlation is zero against the alternative that it is not equal to zero. As C5b-9 levels and platelet count are assumed to be predictive for the clinical course of the patients, the association with secondary endpoints will be assessed. Moreover, as C5b-9 and platelet count will be documented at the study time points T0 to T8, their evolution over time will be analyzed using a linear mixed-effects model.

Sample size estimation

To the best of our knowledge, no study is available reporting the association of complement activity and change of platelets in cardiac patients. However, Qin et al. (4) reported a strong correlation (Pearson's correlation coefficient) of $r=0.683$ between platelets (MPV/PTC ratio) and mtDNA levels in 68 patients who underwent CABG. As mtDNA levels are strongly associated with complement activation (9), we expect to observe a comparable correlation between the change of platelets and complement activation. Power analysis was performed to determine the sample size for Spearman's correlation using G*Power (version 3.1.9.2). Assuming an effect size corresponding to $r=0.683$, a sample size of 162 has a power of 95% to assess a significant difference from a large effect of $r=0.5$ with a type I error at a global 5% level (two-tailed). To account for drop-outs, a total of 190 patients will be included.

Secondary analysis

All secondary parameters will be summarized using descriptive statistics, i.e. no./total no. (%) for categorical variables and median (25th to 75th percentile) or mean (SD), however appropriate.

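### The primary endpoint correlates uncorrected before-and-after-bypass changes in two blood concentrations, so haemodilution is mixed with platelet loss and complement activation, with a net effect whose direction is not determined

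*Protocol*

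**What the plan says.** Protocol section 3.4 defines the primary endpoint as "the correlation of the change of C5b-9 and change of platelet count from baseline (T0) to after 15 minutes of administration of protamine (T2"; the synopsis repeats it. Section 7 adds "The two changes (C5b-9 and platelet count) are continuous variables and their correlation" and tests it with a plain Spearman test of rho = 0, two-sided, in all patients who have the measurements. It does not say whether change is absolute or relative.

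Section 3.2 fixes the sampling times: "T0 baseline: after insertion of arterial cannula beginning surgery" and "T2 15 minutes after protamine infusion". Section 4.1 requires surgery "on cardiopulmonary bypass (CPB"), so the bypass run lies between the two samples in every patient.

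The scientific question concerns loss of platelets. Section 1.1 says "it is still unclear whether the activation of the complement system further increases platelet loss", and section 1.2 states "We hypothesize that increased complement activation during CPB leads to platelet activation and loss of platelets".

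The protocol does not mention haemodilution, haematocrit or any correction for them. Section 3.3.2 lists "whole blood cell count, standard plasmatic coagulation tests, blood gas analysis" among routine parameters, which would normally contain a haematocrit, but these are collected only where available. CPB details, cell-saver volume and transfusions are also recorded. None of these enters the primary analysis.

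**The concern.** Between T0 and T2 the patient's blood is mixed with circuit prime and infused fluid. That lowers the platelet count without any platelet being lost, and it lowers measured C5b-9 without any less activation. The two changes therefore share a component that is neither of the quantities in the hypothesis.

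What matters most is how dilution varies between patients. A more diluted patient shows a larger platelet fall and a smaller C5b-9 rise, which pushes the signed changes towards a positive correlation, against the hypothesis. If the same patients also have more activation, for example because of a longer bypass run, the larger platelet fall coincides with more C5b-9 and the push is the other way. A null result might hide a real link, and a significant inverse correlation might be partly or wholly dilution.

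The pathway objective in section 2.2 is exposed too. C1q, MBL and Factor B are native components, and dilution alone lowers their levels, which could be read as consumption.

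**Working it through.** **The plan's own figure.** By Fisher z, n = ((1.960 + 1.645)/(atanh 0.683 - atanh 0.5))² + 3 = (3.605/(0.8347 - 0.5493))² + 3 = 162.5. The stated 162 evaluable patients at 95% power reproduces, and this point does not touch it. For the test of rho = 0 at n = 162, power is about Φ(atanh(r)·√159 - 1.96): 72% at |r| = 0.20, 48% at 0.15 and 24% at 0.10.

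**Model.** C5b-9 at T2 = C0 × A × D and platelets at T2 = P0 × R × D, where A is the true fold rise, R the true platelet retention and D the dilution factor.

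**Inputs, all assumed because the documents give none.** D mean 0.75, SD 0.05 or 0.10; A median 4, log-SD 0.5; R about 0.80, log-SD 0.15; baseline platelets 220 (SD 50) G/L; baseline C5b-9 log-SD 0.4. There were 200,000 simulated patients per setting. In the linked columns, more dilution goes with more activation (r = 0.5), and dilution is related to retention only through activation.

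**Spearman correlation of absolute changes:**

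| True log-scale correlation | No dilution | D = 0.75 in all | Independent, SD 0.05 | Independent, SD 0.10 | Linked, SD 0.05 | Linked, SD 0.10 |
|---|---|---|---|---|---|---|
| -0.50 | -0.39 | -0.30 | -0.25 | -0.13 | -0.36 | -0.32 |
| -0.30 | -0.23 | -0.18 | -0.14 | -0.03 | -0.25 | -0.24 |
| 0 | 0.00 | 0.00 | +0.03 | +0.12 | -0.10 | -0.11 |

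Three things follow.

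1. Independent dilution moves an inverse correlation towards zero and turns a true zero positive.
2. Linked dilution gives a negative correlation where there is none.
3. Part of the first-row drop is a scale effect. Identical dilution in everyone already moves -0.39 to -0.30. At SD 0.05, that 0.09 is more than half of the total drop of 0.14. Identical dilution would leave the ranks of relative changes untouched.

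**Relative changes, a wider set of assumptions.** D mean 0.70, SD 0.05 to 0.10; fold rise 1.5 to 5, log-SD 0.2 to 0.6; retention 0.80, SD 0.10; dilution unrelated to retention. A dilution-free -0.67 becomes -0.51 to +0.08 with independent dilution and -0.81 to -0.30 with linked dilution. A true zero becomes +0.06 to +0.42 and -0.21 to +0.18 respectively. The sign of the distortion changes within the assumed range.

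**Which correction.** If red-cell volume is unchanged, whole blood is diluted by Hct0/Hct2 and plasma by (Hct0/Hct2) × (1 - Hct2)/(1 - Hct0). Example with assumed values: 5 L blood, haematocrit 0.40, 1.5 L cell-free fluid added. Then Hct2 = 2/6.5 = 0.308. The whole-blood factor is 6.5/5 = 1.30 and the plasma factor is 4.5/3 = 1.50. Correcting a plasma protein by 1.30 leaves it at 1.30/1.50 = 0.87, which is 13% low with no consumption.

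**Does correction help?** With a 4% error in the haematocrit ratio, the corrected absolute-change correlation was about -0.35 (true -0.50), -0.20 (true -0.30) and +0.01 to +0.03 (no link) in every dilution setting, independent or linked. This also held when C5b-9 was diluted and corrected by the plasma form (baseline haematocrit assumed 0.40, SD 0.04).

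**The case against.** The strongest counter-argument is that every dilution figure is assumed, that derivation of laboratory variables and adjusted analyses are often left to a statistical analysis plan, and that the data for an adjustment are already on the collection list. The synopsis also words the primary objective as impact on platelet count, which an uncorrected count does describe.

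Part of this stands: the size cannot be settled from the documents. The rest does not remove the point. The protocol itself fixes both the endpoint and the test, and sections 1.1 and 1.2 ask about loss. A haematocrit that was not recorded because it was not available cannot be recovered later.

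A reader might infer that dilution necessarily biases the correlation towards zero, so that a significant inverse result would be understated. The documents do not support that. It requires dilution to be independent of activation, which nothing in the protocol establishes, and section 1.2 itself attributes activation to bypass. A reader might also infer that most of the platelet fall is dilution. With a mean factor of 0.75 and retention of 0.80, dilution alone would give 0.25 of a 0.40 fractional fall, but both inputs are assumptions.

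It is also fair to say that a single haematocrit ratio is wrong for plasma proteins, that red cells, cell-saver blood and bleeding distort the ratio, and that a partial Spearman correlation adjusted for dilution would be a defensible alternative.

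**Conclusion.** The point holds. As defined, the primary endpoint mixes shared haemodilution with true platelet loss and complement activation, and the net direction of the distortion is undetermined. Neither a null nor a significant result could be read cleanly as an answer to the study's question.

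The mechanism follows from the sampling times, the use of bypass in all patients and the absence of any correction. The size does not: the figures above are illustrations that depend on the assumed spread of dilution, its relation to activation and the scale of change. Within those assumptions the shift ranges from minor to large enough to matter. A correlation attenuated to 0.10 would be detected in about 24% of studies with 162 patients, and one of 0.15 arising from dilution alone would be declared significant in about 48%. The sample-size arithmetic is not in question here.

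**What to change.** In sections 3.4 and 7, base the T0-T2 changes on dilution-corrected T2 values:

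- Platelet count: T2 value × Hct0/Hct2.
- C5b-9 and the other complement factors, if measured in plasma or serum: T2 value × (Hct0/Hct2) × (1 - Hct2)/(1 - Hct0). Apply this before reading a fall in C1q, MBL or the other factors as consumption.
- Report the uncorrected correlation alongside.
- In section 3.3.2, require haematocrit to be recorded at T0 and T2 for every patient.
- Repeat the analysis without patients given red cells, platelets, plasma or cell-saver blood before T2.

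The cost is wording in the two sections, one recording requirement and derived variables from samples already scheduled at both times. The downside is small: the correction is imperfect in patients given those products before T2, which the repeat analysis covers. Patient care is unaffected.

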3.5. Secondary Study Endpoints

- levels of complement activation: c5b-9, C1q (C1r/C1s), C3a, C5a, MBL, Factor B, Factor D
- Levels of mtDNA
- platelet function as measured by FACS
- Levels of coagulation factors FI – FXIII, FXa, FXIIa, Kallikrein, Bradykinin, endogenous thrombin potential (ETP)
- transfusion requirements (red blood cell concentrates, fresh frozen plasma, platelet concentrate) and dosages of coagulation products administered during surgery, at ICU and until POD 3

- Need for revision surgery because of re-bleeding or hematoma formation **within** the first 24 hours at ICU
- hours/days on mechanical ventilation
- Oxygenation index (Horowitz quotient) during surgery, at ICU until POD 3 if applicable
- length of ICU stay
- length of hospital stay
- postoperative complications:
 - single and multiple organ failure according to SOFA score
 - acute kidney injury (RIFLE score)
 - diagnosed infection and sepsis
- incidence and type of cardiovascular thromboembolic events
- in hospital mortality

3.6. Number of patients

190 patients will be included after written informed consent.

3.7. Timetable

The duration of the planned recruitment phase is 2 years. For the single subject the duration of the participation 72 hours in the active phase and further 27 days (until 30 days after inclusion) in the Follow-Up phase.

ISSUE	Time schedule
Submission to the EC:	
Study Conduction:	
Laboratory Analysis:	
Final Report / Publication:	

4. STUDY POPULATION

All adult patients undergoing elective coronary artery bypass graft surgery with written informed consent meeting the following criteria:

4.1. Inclusion criteria:

- I.1. Male and female subjects > 18 years and < 86 years
- I.2. elective coronary artery bypass graft surgery **with or without valve surgery (max. 2 valves)** and **elective valve surgery (max. 2 valves)** on cardiopulmonary bypass (CPB)
- I.3. ASA I - IV
- I.4. written informed consent

4.2. Exclusion criteria:

- E.1. emergency CABG **with or without cardiac valve surgery and emergency valve surgery and emergency aortic dissection**
- E.2. preexisting complement deficiency syndromes
- E.3. preexisting thrombocytopathy or thrombocytopenia (platelet count below 100 G/L)
- E.4. Known history of congenital coagulopathy
- E.5. Patients that are known to be pregnant
- E.6. Known participation in another interventional clinical trial

5. FURTHER STUDY PROCEDURES

5.1. Patient Withdrawal (Drop-out)

Patients can drop-out of the study by their own request or the request of the patient's authorized person or the patient's legal guardian (whenever applicable) without mentioning any reasons and without any consequences for the subsequent treatment. Moreover, patients can be withdrawn from the study by the Investigator for health risk reasons.

If the investigator decides to withdraw the patient from the study the reason will be documented in the CRF. It includes, but is not limited to:

- Withdrawal of consent/ not giving consent
- Lost to Follow-Up, etc

If the patient decides to be withdrawn from the study the patient will be asked to agree to use the data collected in course of the study. The patient's decision will be recorded in the patient's medical file.

5.2. Discontinuation of the Study

The Sponsor is authorized to discontinue the study because of relevant medical/administrative causes. The reasons for the discontinuation of the study have to be documented in detail. Patients who are still enrolled at the time of discontinuation, have to be examined for a final investigation, which will be documented in the CRF. If the Investigator has any ethical qualms concerning the continuation of the study, this has to be immediately reported to the Sponsor.

The Sponsor is authorised to discontinue the study, if:

- The recruitment rate of patients is not sufficient
- Serious, non-resolvable problems of quality of the collected data evolve
- New scientific findings during the study's run-time do not allow a continuation of the study

5.3. Closure of the Study

The study must be closed after completion and the ethics committees will be informed when the study is closed.

6. DOCUMENTATION AND DATA MANAGEMENT

The accomplishments of the study in agreement with the GCP-guidelines as well as the trueness of all data documented in the CRF are the responsibility of the Investigator. All collected data of this study have to be recorded in the CRF by appropriate authorized persons.

The Investigator records the participation in a special identification list of patients. Additionally, the participation of the patient in this clinical study has to be recorded in the patient chart.

6.1. Data Entry Form (CRF)

Data of patients and investigation results will be recorded into Case Report Forms (CRF), which are especially developed for this study.

Only the use of black ball pens is allowed. Corrections have to be made in such a way, that previous entries remain readable. Corrections have to be signed and dated by the authorized person, who made the corrections. Data which are not available or were not collected, have to be clearly identifiable as such (NA and ND). The reasons should be documented, if necessary.

6.2. Data Management

Data items from the CRF are entered centrally into the study database by authorized data management staff using appropriate entry techniques and probability check. Entered data are systematically checked by data management staff, using error messages printed from validation programs and database listings. Obvious errors or omissions are corrected by the data management personnel. After recording of all entries and clarification of all queries, the database will be closed at the completion of the study. This closure has to be documented.

7. STATISTICS

Primary analysis

The primary endpoint of this study is the correlation of the change in C5b-9 and the change in platelet count from baseline (T0) to 15 minutes after administration of protamine (T2). The analyzed study population will consist of all patients with available measurements necessary to assess the primary endpoint.

The two changes (C5b-9 and platelet count) are continuous variables and their correlation (Spearman's rank-order correlation denoted by ρ) will be assessed. Therefore, the hypotheses

$$H_0: \rho = 0 \quad \text{vs.} \quad H_1: \rho \neq 0$$

will be tested using the Spearman rank-order correlation test, i.e. the null hypothesis that the Spearman correlation is zero against the alternative that it is not equal to zero. As C5b-9 levels and platelet count are assumed to be predictive for the clinical course of the patients, the association with secondary endpoints will be assessed. Moreover, as C5b-9 and platelet count will be documented at the study time points T0 to T8, their evolution over time will be analyzed using a linear mixed-effects model.

Sample size estimation

To the best of our knowledge, no study is available reporting the association of complement activity and change of platelets in cardiac patients. However, Qin et al. (4) reported a strong correlation (Pearson's correlation coefficient) of $r=0.683$ between platelets (MPV/PTC ratio) and mtDNA levels in 68 patients who underwent CABG. As mtDNA levels are strongly associated with complement activation (9), we expect to observe a comparable correlation between the change of platelets and complement activation. Power analysis was performed to determine the sample size for Spearman's correlation using G*Power (version 3.1.9.2). Assuming an effect size corresponding to $r=0.683$, a sample size of 162 has a power of 95% to assess a significant difference from a large effect of $r=0.5$ with a type I error at a global 5% level (two-tailed). To account for drop-outs, a total of 190 patients will be included.

Secondary analysis

All secondary parameters will be summarized using descriptive statistics, i.e. no./total no. (%) for categorical variables and median (25th to 75th percentile) or mean (SD), however appropriate.

Explorative data analyses will be performed as applicable to investigate the relationship between the comprehensive measurements. These might involve standard explorative techniques such as factor analysis (FA), principal component analysis (PCA), multiple factor analysis (MFA), homogeneity analysis and different clustering approaches as well as more recently developed techniques arising in the context of machine learning.

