Objective	
Primary:
 
-To assess the impact of complement activation on platelet count.
 
Secondary:
 
- To assess the specific pathway of complement activation, mtDNA levels and their effects on platelet count and platelet function using mean platelet volume to platelet count ratio (MPV/PTC) and specific platelet function by fluorescence-activated cell sorting (FACS).
 
- To explore whether these variables correlate with transfusion requirements, postoperative morbidity (need for revision surgery, cardiovascular events including thromboembolic events, sepsis, single or multiple organ failure according to SOFA Score) and in hospital mortality.

Endpoints and Evaluation Parameters	
Primary endpoint:
 
- Correlation of the change of C5b-9 and change of platelet count from baseline (T0) to after 15 minutes of administration of protamine (T2).
 
Secondary endpoints:
 
- correlation between levels of complement factors [c5b-9, C1q (C1r/C1s), C3a, C5a, MBL, Factor B, Factor D], mtDNA level [human NADH dehydrogenase 1 gene] and platelet function [MPV/PTC ratio and FACS for platelet activation factor 4 (PAF-4)]
 
- correlation between levels of complement [see above] and concentration of coagulation factors [F I – F XIII, FXa, FXIIa, Kallikrein, Bradykinin, endogenous thrombin potential (ETP)] and transfusion requirements
 
- correlation of levels of complement, mtDNA and platelet function to postoperative morbidity (need for revision surgery, cardiovascular events including thromboembolic events, sepsis, single or multiple organ failure according to SOFA Score) and in hospital mortality

Number of Patients	190

Duration of Patient Participation	- day of surgery to postoperative day three (POD 3) - Follow-Up Period "Medical Monitoring": until discharge or day 30
Dates of Beginning and End of Study	Date of beginning of study: 1.July 2018 Date of end of study: 1.July 2020
Inclusion Criteria	I.1. Male and female subjects \geq 18 years and \leq 85 years I.2. elective coronary artery bypass graft surgery on cardiopulmonary bypass (CPB) with or without valve surgery (max. 2 valves) and elective valve surgery (max. 2 valves) I.3. ASA I - IV I.4. written informed consent

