2.2. Further Study Objectives

A secondary aim of the study is to investigate the specific pathway of complement activation, the mtDNA levels and the interaction with platelet function.

Therefore we search for correlations between levels of complement factors [c5b-9, C1q (C1r/C1s), C3a, C5a, MBL, Factor B, Factor D], mtDNA level [human NADH dehydrogenase 1 gene] and platelet function [MPV/PTC ratio and FACS for platelet activation factor 4 (PFA)].

Further it will be explored whether the level of complement activation and levels of mtDNA and the plasmatic coagulation system correlate with transfusion requirements, postoperative morbidity (need for revision surgery, cardiovascular events including thromboembolic events, sepsis, single or multiple organ failure according to SOFA Score), and in hospital mortality.

We will correlate levels of complement [see above] and concentration of coagulation factors [F I – F XIII, FXa, FXIIa, Kallikrein, Bradykinin, endogenous thrombin potential (ETP)] and transfusion requirements and correlate levels of complement, mtDNA and platelet function to postoperative morbidity (need for revision surgery, cardiovascular events including thromboembolic events, sepsis, single or multiple organ failure according to SOFA Score) and in hospital mortality.

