10. SCORES

SOFA

The SOFA is a six-organ dysfunction/failure score which is daily assessed. Each organ is graded from 0 (normal) to 4 (the most abnormal), providing a daily score of 0 to 24 points. Single organ failure is defined as SOFA score >2 for one organ and multiple organ daily arises with at least 2 organ systems with >2 points.

EUROSCORE II

The abbreviation stands for European System for Cardiac Operative Risk Evaluation and calculate the estimated pre-operative mortality by using the following factors which can be seen in the graphic below.

EuroSCORE II

Patient Related Factors

- Patient Age (years): 18-95
- Gender: Male / Female
- Creatinine Clearance (ml/min) or Dialysis:

> 85	51 - 85	< 51	Dialysis
------	---------	------	----------
- Calculate Creatinine Clearance
- Extracardiac Arteriopathy: Yes / No
- Poor Mobility: Yes / No
- Previous Cardiac Surgery: Yes / No
- Chronic Lung Disease: Yes / No
- Active Endocarditis: Yes / No
- Critical Preop State: Yes / No
- Diabetes on Insulin: Yes / No

Cardiac Related Factors

- NYHA Class: I / II / III / IV
- CCS Class 4 Angina: Yes / No
- LV Function (EF):

< 21%	21 - 30%	31 - 50%	> 50%
-------	----------	----------	-------
- Recent MI: Yes / No
- PA Systolic Pressure (mm Hg):

< 31	31 - 55	> 55
------	---------	------

Operation Related Factors

- Urgency: Elective / Urgent / Emergent / Salvage
- Thoracic Aortic Surgery: Yes / No
- Weight of the Intervention: (see key below)

1	2	3	4
---	---	---	---
- 1. Isolated CABG 3. Two procedures
- 2. Single non CABG 4. Three + procedures

Tap Any Label For Definition

Estimated Mortality:

Calculate Risk

Add to Database **Stored Patients** **Email Patient Data**

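### Marker-outcome aims are worded only as correlation or association and EuroSCORE II has no analytic role, so the planned results cannot show prediction beyond known preoperative risk

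*Protocol*

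**What the plan says.** **How the outcome aims are worded.** The synopsis gives a secondary objective "To explore whether these variables correlate with transfusion requirements, postoperative morbidity" and in-hospital mortality. It lists as a secondary endpoint the "correlation of levels of complement, mtDNA and platelet function to postoperative morbidity" and in-hospital mortality. Section 2.2 repeats this: "Further it will be explored whether the level of complement activation and levels of mtDNA and the plasmatic coagulation system correlate with transfusion requirements", and also morbidity and death.

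**What section 7 adds.** For C5b-9 and platelet count the stated premise is that "C5b-9 levels and platelet count are assumed to be predictive for the clinical course of the patients", from which it follows that "the association with secondary endpoints will be assessed". This sentence does not cover mtDNA, which enters through the synopsis and section 2.2. Under the secondary analysis, "All secondary parameters will be summarized using descriptive statistics". A list of optional exploratory techniques follows (factor and component analysis, clustering, machine learning). No outcome model with covariates is named.

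**Where EuroSCORE II appears.** It is a baseline item in the synopsis, the flow chart and section 3.3.2 ("pre-medication, Euroscore II"). Section 10 describes its purpose: to "calculate the estimated pre-operative mortality by using the following factors". It is absent from the objectives, the endpoints and section 7.

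**The concern.** Preoperative risk is a plausible common cause of the markers and of the outcomes, and the protocol's own content points that way. Section 4.1 admits patients from isolated bypass grafting to grafting plus two valves, ASA I to IV. Section 1.1 attributes complement activation to blood meeting foreign surfaces on bypass, so more extensive surgery plausibly means more C5b-9 and more platelet loss. The EuroSCORE II items shown in section 10 include the weight of the intervention, age, renal function and left ventricular function, all of which plausibly bear on transfusion, organ failure and death.

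An unadjusted correlation therefore mixes the marker's own information with risk known before the first incision. This matters for how the results will be read: section 1.3 hopes that they may lead to therapies that limit complement activation and so reduce bleeding. That step needs an association that goes beyond preoperative risk.

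**Working it through.** **1. The plan's own figure.** Section 7 states r = 0.683 against r = 0.5, two-sided 5%, power 95%, n = 162. By Fisher z:

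n = ((1.960 + 1.645) / (atanh 0.683 − atanh 0.5))² + 3 = (3.605 / (0.8347 − 0.5493))² + 3 = 162.5.

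The stated 162 reproduces (power 94.9%, or 95.0% with the usual small bias term). It concerns the primary correlation only and does not change with this point. Enrolment of 190 leaves room for 1 − 162/190 = 14.7% drop-out, so 162 is taken below as the evaluable number.

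**2. Size of the problem, continuous outcome (illustration).** The documents give no correlation of any marker or outcome with preoperative risk, so these inputs are assumptions:
- a = correlation of marker with risk score
- b = correlation of outcome with risk score
- no link between marker and outcome except through risk

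The marker-outcome correlation is then ρ = a × b. The chance that an unadjusted Spearman test is significant at 5% is approximately Φ(d − 1.96) + Φ(−d − 1.96), where d = atanh(ρ) × √((n − 3)/1.06).

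Worked case, a = 0.3 and b = 0.4: ρ = 0.12, atanh ρ = 0.1206, d = 0.1206 × √(159/1.06) = 1.477, giving 31%.

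A simulation of 4,000 data sets per case at n = 162 compared the unadjusted with the partial Spearman test:

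| a | b | ρ | Formula, unadjusted | Simulated, unadjusted | Simulated, adjusted |
|---|---|---|---|---|---|
| 0.2 | 0.3 | 0.06 | 11% | 10% | 4% |
| 0.3 | 0.3 | 0.09 | 20% | 20% | 5% |
| 0.3 | 0.4 | 0.12 | 31% | 31% | 4% |
| 0.4 | 0.4 | 0.16 | 51% | 49% | 5% |

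**3. Rare binary outcomes.** With event rate p, the Spearman correlation between a continuous score and a yes/no outcome cannot exceed √(3p(1 − p)). Section 1.2 gives about 2% to 8% for bleeding that requires transfusion and even reoperation:
- p = 0.02: √(3 × 0.02 × 0.98) = 0.24
- p = 0.08: √(3 × 0.08 × 0.92) = 0.47

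These ceilings need perfect separation. If the score discriminates with an AUC of 0.8 (assumed), b = (2 × 0.8 − 1) × ceiling = 0.15 to 0.28. With a = 0.3, ρ is 0.044 to 0.085, and the same formula at n = 162 gives about 8% to 18%. The table above must not be carried over to such outcomes.

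**The case against.** The strongest reply is that the plan is silent here, not wrong. A reader might infer that the protocol has chosen a raw analysis. It has not: section 7 names no model for these endpoints, never says unadjusted and rules no covariate out. Covariates for exploratory aims are commonly left to a statistical analysis plan, which may exist. That EuroSCORE II goes unused is thus true of this protocol only. This limits the point but does not remove it, because the endpoints are themselves worded as two-variable correlations and section 7 presumes prediction.

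A reader might also infer that a marker merely tracking preoperative risk would be wrongly called predictive. In the plain sense it does predict. What an unadjusted result cannot show is independent or added prediction, or causation. The outcome aims, which are exploratory, do not claim these outright.

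Two further objections stand. All correlations in the illustration are assumed. And EuroSCORE II, as shown in section 10, contains the weight of the intervention but no bypass duration, so adjusting for it does not close the whole pathway through length of surgery. Details on bypass are collected separately under section 3.3.2.

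**Conclusion.** The point holds for the secondary marker-outcome aims. As worded, they yield associations that cannot be told apart from preoperative risk, although a baseline measure of that risk is already collected. They can support a statement of unadjusted exploratory association, and nothing stronger.

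The size cannot be read from the documents. Under the assumed correlations, with a continuous outcome and 162 evaluable patients, a marker with no relation of its own would be significant in about 10% to 49% of studies without adjustment and in about 5% with it. For binary outcomes as rare as 2% to 8% the excess is smaller.

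Nothing here touches the primary test of change in C5b-9 against change in platelet count, or the sample size. The matter is worth correcting because the better method is cheap, not because the study is compromised.

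**What to change.** Add to section 7:

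- Report each association of complement, C5b-9, platelet count, platelet function or mtDNA with a clinical outcome twice: unadjusted, and adjusted for EuroSCORE II as one continuous covariate.
- For continuous or count outcomes (transfused units, durations), use partial Spearman correlation or regression. For binary outcomes, use penalised logistic regression where event counts allow.
- Rest any claim of independent prediction on the adjusted result. Where none is available, call the finding an unadjusted exploratory association.
- Say that the adjusted result accounts for preoperative risk only, since EuroSCORE II does not include bypass duration.

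The cost is a few sentences and one variable already on the case report form. The adjustment uses one degree of freedom and needs no change to 162 or 190. Its drawback is limited use for the rarest outcomes, where there may be too few events to model. It should be fixed before the marker-outcome data are analysed, so that the choice of covariate is not made with the results in view.
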